2. OBJECTIVES

2.1 Primary Objective

To evaluate the response rates (PSA responses and changes in PSADT) following immunization with the Ad/PSA vaccine using a prime-boost immunization strategy, in patients with hormone refractory metastatic disease.

2.2 Secondary objectives

- 2.2.1 To evaluate the development of anti-PSA immune responses in study patients.
- 2.2.2 To evaluate biochemical (PSA recurrence) and radiographic (bone scans) time to progression and overall survival in evaluable patients receiving the Ad/PSA vaccine.

3. SELECTION OF PATIENTS

As described in Section 1.6 prostate cancer patients with hormone refractory metastatic disease will be enrolled in the study.

3.1 Inclusion criteria:

- 3.1.1 Men with prostate cancer who present with evidence of hormone refractory disease (D3).
- 3.1.2 Men with a positive bone scan or a positive CT scan (with obvious soft tissue metastasis or lymph nodes >1 cm), a PSA doubling time of ≥6 months, and a total PSA of <10 ng/ml, and asymptomatic OR men with a negative bone scan and a negative CT scan with any PSA doubling time and asymptomatic.
 - 3.1.3 Scans must be obtained within 6 weeks of initiation of treatment.
 - 3.1.4 Written informed consent.
 - 3.1.5 Age > 18 years.
 - 3.1.6 Required laboratory values (obtained within 2 weeks of initiation of treatment)
 - 3.1.6.1 Serum creatinine < 2.0 mg/dL
 - 3.1.6.3 Adequate hematologic function: granulocytes \geq 1800 per mm³, platelets \geq 100,000 per mm³, WBC >3700, and lymphocytes >590.
 - 3.1.6.4 Adequate hepatocellular function: AST <3x ULN and total bilirubin <1.5 mg/dl (unless bilirubin elevation is consistent with Gilbert's syndrome).

- 3.1.6.5 Castrate levels of testosterone of ≤50 ng/ml.
- 3.1.7 PSA used as an eligibility criterion must be drawn within 28 days prior to injection number 1 and will be redrawn on Day 1 for use as a baseline value.
- 3.2 Exclusion criteria:
 - 3.2.1 Active or unresolved clinically significant infection.
 - 3.2.2 Parenteral antibiotics <7 days prior to initiation of treatment.
 - 3.2.3 Evidence of prior or current CNS metastases. Specific imaging is not necessary in the absence of signs or symptoms.
 - 3.2.4 Co-morbid medical conditions which would result in a life expectancy (participation) of less than 1 year.
 - 3.2.5 Patients with compromised immune systems; congenital, acquired, or drug-induced (immunosuppressive agents) will be excluded from the study. Use of prednisone at doses higher than 10 mg daily (or equipotent steroid doses) for more than 7 days within 3 months of initiation of treatment is not allowed.
 - 3.2.6 Pre-existing malignancies that required treatment within the past 5 years except for basal or squamous cell cancers of the skin.
 - 3.2.8 Prior participation in any vaccine studies for non-infectious diseases.
 - 3.2.9 Prior chemotherapy, defined as prior cytotoxic chemotherapy for prostate cancer (or any cancer unless more than 5 years have elapsed). Examples of cytotoxic chemotherapy are mitoxantrone/prednisone and taxanes. Drugs such as Casodex or ketoconazole treatment must have been completed at least 6 weeks prior to initiation of treatment.
 - 3.2.10 The inability to understand the English language and the clinical protocol.
 - 3.2.11 Allergy or religious objection to pork products; Gelfoam is produced from pork.

Patients that have been on bisphosphonate treatment for greater than 1 month prior to entry into the trial will be able to continue the medication. Patients that have not been on bisphosphonate therapy will not start on the medication for at least 30 days after the first vaccination.

4. Registration Procedures

- 4.1 All patients will be registered through the Department of Urology at the University of Iowa Hospitals and Clinics (UIHC) or the Urology Service at the Iowa City Veterans Affairs Health Care System (ICVAHCS).
- 4.2 Patients who are candidates for enrollment into the study will be evaluated for eligibility by the clinical investigators to ensure that the criteria outlined in Section 3 have been satisfied and that the patient is eligible for participation in this clinical investigation. The University of lowa will provide a patient eligibility case report form for this evaluation.

- 4.3 Informed Consent Signed informed consent for enrollment in this protocol will be obtained from eligible patients by the attending physician, study coordinator, or clinical trial coordinator before the start of research intervention. At the preadmission consultation, patients will be fully informed of the purpose and potential risks and benefits of participating in the study. Patients have the opportunity to have questions answered to their satisfaction before signing the consent.
- 4.4 Eligible patients must be registered Monday through Friday between 8:00 a.m. and 4:30 p.m. (Central Time). Patients at the University of Iowa Clinical Cancer Center will be registered by calling [name], MA at [contact]. Patients at the ICVAHCS will be registered by calling [name] [name], PhD at [contact], [name]. Information from the eligibility form will be provided by the investigator or the investigator's research staff to the University of Iowa Cancer Center at this time, and the patient will be registered and assigned a unique patient number.
- 4.5 No patient may be enrolled or begin research intervention prior to registration and assignment of a patient number. As a follow-up, University of Iowa Cancer Center will provide the investigator with written confirmation of each patient's registration.
- 4.6 All investigators will be notified by the Chair of the Protocol Review and Monitoring Committee or by the trial's Data and Safety Monitoring Board if the study is placed on administrative hold, and when the study is completed or closed to further patient enrollment.
- 4.7 Patients must begin the vaccine protocol within 30 days of registration (date the study committee approves patient eligibility).

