1. INTRODUCTION

1.1 Background- Immunotherapy in Prostate Cancer

Prostate cancer is the second leading cause of cancer death among males in the United States. There will be an estimated 234,460 new diagnoses of prostate cancer made in the United States in 2006 (1). Treatments for organ-confined prostate cancer include radical prostatectomy and radiation therapy. When the cancer presents de novo, or recurs outside the prostate, first-line systemic treatments typically include hormonal blockade (with LHRH agonists or bilateral orchiectomy), which suppress testosterone levels, limit the growth of androgen-dependent cancer cells, and result in clinical tumor control. After a median time of 2 years, patients progress into a clinical hormone-refractory state, when the prostate specific antigen (PSA) levels rise despite castration, there is proliferation of androgen-independent cancer cells, and there is continued clinical tumor growth that becomes fatal. Therapeutic measures in this situation include further hormonal manipulations or the use of systemic chemotherapy, which has recently shown a small survival benefit in phase III trials. Approximately 30,000 Americans die from prostate cancer each year.

Immunotherapeutic approaches against prostate cancer have been investigated for several years. Most of these studies have concentrated on active non-specific therapy and adoptive or passive therapy, with only recent focus on the induction of antigen-specific immune responses. Viral vectors have been used successfully in both gene transfer and vaccine therapy studies (2). Replication-competent and replication-deficient adenoviruses expressing foreign proteins have been used to elicit immune responses to a variety of tumor antigens (3-7).

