8 STUDY PARAMETERS

- 8.1 Scans or x-rays used to document measurable or evaluable disease must be done with 6 weeks prior to the initiation of treatment.
- 8.2 CBC with differential, LFT's must be done ≤2 weeks before study entry. Castrate levels of testosterone must be drawn at initiation of treatment.
- 8.3 All chemistries must be done <2 weeks before the study entry, unless specifically required on day 1 as per protocol. If abnormal, they can be repeated within 48 hours prior to the initiation of treatment.
- 8.4 Hgb, Hct, WBC, Plt must be done <2 weeks before study entry but, if abnormal, they can be repeated <48 hours prior to initiation of treatment.
- 8.5 REMOVAL OF PATIENTS FROM STUDY (Criteria for discontinuation of a patient's study participation)
 - 8.5.1 Adverse events: Study subjects will be monitored for adverse events for 30 days beyond the final study injection, or longer if existing unresolved AEs are being monitored. In the event of a vaccine-associated unmanageable or irreversible toxicity, that would include hematological and non-hematological toxicities, the investigator will withdraw a patient from further research intervention and notify the Study Chair immediately. In addition, the FDA and the IRB and other agencies listed on page 17 will be notified of the adverse events. If unmanageable or irreversible toxicities occur the patients will receive the best possible medical care according to the recommendations of the treating physicians. The treatment plan will depend upon what unmanageable or irreversible toxicities may occur. In the event of an emergency the patient will be instructed to seek immediate care by calling 911, his local physician, the University of Iowa or Iowa City VA Health Care System urology staff on call.

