	Std. of Care or Res.	Prior to Reg. ¹	Day 1 First Inj.	30 d. 2 nd Inj.	44 d.	60 d. 3 rd Inj.	74 d.	90 d.	6 mo	9 mo	12 mo	18 mo.	24 mo.	Annual to prog.	Follow- up ⁷
Immunization ²	R		X	X		X									
Physical Examination	S		X	X		X		X							
Adverse Event Assessments	R		X	X		X		X							
Performance Status	S		Х	Х		X		X	X	X	Х				
Vital Signs	S		X	X		X		Χ	X	X	Х				
Weight	S		Х	Х		X		Χ	Х	Х	Х				
Blood for PSA & PAP ³	S/R		Х	X (R)		X(R)		Χ	Х	Х	Х	Х	Х		
anti-PSA Ab, and lymphocytes for cellular immunity	R	Х	Х	Х	Х	Х	Х	Х	X _e	X ⁶	X ₆	Х	Х		
CBC, differential	R	Х		Х		X		Х	Х	Х	Х	Х	Х		
AST, ALT, LDH, alkaline phosphatase, bilirubin	R	Х		Х		Х		Х							
Creatinine	R	Х		Х		X		Х							
Urinalysis	R	Х		Х		X		Х							
Serum testosterone	R	Х													
Chest x-ray	R	Х		X ⁴		X ⁴		X ⁴							
Bone scan	S	Х						Х	Х		Х		Х	Х	
Abdominal/pelvic CT	S	Х							X ⁵		X ⁵				
Survival assessment	R														X ⁷

S = Procedures considered "Standard of Care" for prostate cancer patients.

R = Procedures considered "Research" as part of this Clinical Trial.

In the event of holidays or other extenuating circumstances the times on the table may vary by ± 4 days for the first 90 days. Beyond that every effort will be made to see the patient within 2 weeks of the expected date of return, but the investigator is willing to allow for other arrangements for the convenience of the patient.

¹ Reg. = Registration, the date patient eligibility approved by the study team.

² Androgen deprivation therapy must continue for the duration of study participation.

³ If the PSA meets the definition of progression, partial or complete response, confirm the PSA results >/= 28 days.

⁴ will be repeated only if abnormal at screening or if patient develops a fever.

⁵ will be repeated only if abnormal at screening.

⁶ to be performed even if there is disease progression (up to 12 months from study entry) if the patient has consented to this in the informed consent (question in section "How long will I be on the study?)."

⁷ Follow-up for survival every 6 months by telephone.

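### The testosterone limit in 3.1.6.5 (50 ng/ml, or 5,000 ng/dl) cannot, as written, act as a numeric check of castrate status; its value and unit need to be verified

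*Combined protocol and SAP*

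**What the plan says.** Section 3.1.6.5 lists, among the required laboratory values, "Castrate levels of testosterone of ≤50 ng/ml". No other testosterone limit, reference range or testosterone unit appears in the documents.

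These places bear on the same requirement:

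- Section 3.1.1 requires hormone-refractory (D3) disease. It gives no laboratory test for it. Section 1.1 describes that state as one "when the prostate specific antigen (PSA) levels rise despite castration".
- Section 8.2: "Castrate levels of testosterone must be drawn at initiation of treatment". No number or unit is given.
- Table 6 has one mark for serum testosterone, in the column before registration. Footnote 2 adds: "Androgen deprivation therapy must continue for the duration of study participation".
- Section 4.2 has the clinical investigators review each candidate "to ensure that the criteria outlined in Section 3 have been satisfied".
- Section 7.5.1 defines the primary endpoint as a 50% lengthening of PSA doubling time (PSADT) relative to the patient's own value before enrolment. Sections 5.2 and 10 describe a one-stage efficacy design, and no control arm is planned.

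**The concern.** A criterion labelled as castrate has one task: to separate men whose testosterone is suppressed from men whose testosterone is not. A ceiling does this only if it lies below the values seen in uncastrated men. The figure in 3.1.6.5 appears to lie well above them, so a man with normal testosterone would pass.

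The design makes this matter. Each patient is his own control for PSADT. If testosterone suppression changed between the baseline and follow-up PSA series, PSADT could change for that reason alone, and without a control arm the two causes cannot be separated. Castrate status also helps to define the population: Section 1.6 places men with new recurrences, whether hormone naive or on androgen depletion, in a separate protocol and plans to compare the groups.

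**Working it through.** **Inputs.** The limit of 50 ng/ml comes from 3.1.6.5. The conversion is 1 ng/ml = 100 ng/dl. The upper limit of testosterone in an uncastrated adult man is not in the documents; it is an assumption, varied here from 8 to 30 ng/ml. The plan gives no derivation of its limit, so there is no figure of its own to reproduce.

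**Step 1, conversion.** 50 ng/ml × 100 = 5,000 ng/dl.

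**Step 2, comparison with the assumed upper limit.** A ceiling starts to exclude uncastrated men only when it falls below the top of their range, so the upper end is the relevant comparator. Ratio = 50 / assumed upper limit in ng/ml.

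| Assumed upper limit, ng/ml | Same in ng/dl | Written limit ÷ upper limit |
|---|---|---|
| 8 | 800 | 6.3 |
| 10 | 1,000 | 5.0 |
| 12 | 1,200 | 4.2 |
| 15 | 1,500 | 3.3 |
| 20 | 2,000 | 2.5 |
| 30 | 3,000 | 1.7 |

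Every ratio is above 1. The assumed upper limit would have to exceed 50 ng/ml before the criterion excluded any uncastrated man within the range.

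**Step 3, effect of the unit alone.** The same number per decilitre would be 50 / 100 = 0.5 ng/ml, a factor of 100 lower. This shows how much depends on the unit. It does not show which limit was meant.

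**Step 4, whether another provision supplies the number.** None does:

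- 3.1.1 presupposes castration but does not measure it.
- 8.2 names castrate levels without a figure, so a reader must go back to 3.1.6.5.
- Footnote 2 of Table 6 requires deprivation to continue, not that it be shown to have worked.
- The review in 4.2 applies the Section 3 criteria as they are written.
- Table 6 has no testosterone test after registration. Even if 8.2 means a further draw at the first injection, no later one is planned.

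**Step 5, timing.** Table 6 places the test before registration, the stem of 3.1.6 within 2 weeks of starting treatment, and 8.2 at the start of treatment. Section 4.7 allows up to 30 days between registration and the first injection. A test done before registration can therefore fall outside the 2-week window.

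**The case against.** The strongest reply is that the number does little work in practice. The criterion says castrate in words, 8.2 repeats it, 3.1.1 requires hormone-refractory disease, and deprivation must continue on study. Clinicians review every candidate and may well read the limit as it was intended. This stands against a stronger reading that a reader might infer, namely that hormone-refractory status is not enforced at all. The documents do not support that: the requirement remains in several places, and only its numeric check fails.

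A reader might also infer that the primary endpoint is biased upward. That would need a man who passes 3.1.1, is not castrate, is missed at review, and then has his testosterone suppressed during follow-up. No passage provides for starting or intensifying deprivation on study; footnote 2 speaks only of continuing it. The risk is conditional and cannot be quantified.

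A third inference is that the unit was carried over from PSA, since 3.1.2 uses "a total PSA of <10 ng/ml" while creatinine and bilirubin in 3.1.6 are per decilitre. This is possible but cannot be shown, and the point does not depend on it.

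Finally, the adult range comes from outside the documents. That is true, and it is why the range is stated as an assumption and varied; the conclusion is the same throughout. What the reply does not answer is that no other provision contains a testosterone figure.

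**Conclusion.** The point holds as a fault in one eligibility threshold. It rests on a single assumption, that the upper limit in uncastrated men lies somewhere from 8 to 30 ng/ml. Within that range the number and its label contradict each other, and the trial has no working numeric test of castration.

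The consequence for PSADT is limited to the conditional statement that, in a non-castrate man, a later change in suppression would be confounded with the vaccine. The documents give no basis for how many such men might enrol or how far the response rate would move. Sample size, power and type I error are not affected. The correction should be made, because the limit helps to define the population in which the primary endpoint is read.

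**What to change.** 1. Verify the value and unit in 3.1.6.5, and on the eligibility case report form named in 4.2, against the unit in which the laboratory reports testosterone.
2. Restate the limit in the intended unit, so that the criterion can exclude a non-castrate man. No particular threshold is proposed here; that is for the investigators.
3. Reconcile the restated criterion with 8.2 and Table 6: have 8.2 refer to the same limit, and make the time of the draw agree across 3.1.6, 8.2 and Table 6.
4. If the limit is corrected, recheck the stored screening values of any patients already registered and report any who would not have met it.

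The cost is a short text amendment and a correction to the form if it carries the same figure. The recheck uses results already on file, so it needs no new samples and no change to the sample size.

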1.4 Phase I study

A Phase I clinical trial of the Ad/PSA vaccine has been completed in men with measurable metastatic prostate cancer, with the primary objectives of determining the toxicity profile and maximal tolerated dose (MTD). The ability of the vaccine to induce anti-PSA immune responses and any clinical responses was also evaluated. Funding for the Phase I trial was provided by multiple sources that include the Holden Comprehensive Cancer Center, the Department of Urology, and the Carver College of Medicine at the University of Iowa.

Eligible patients consisted of men with prostate cancer that had measurable metastatic disease, 90% of whom were stage D3. Prior therapies had included androgen depletion, ketaconazole, prednisone, Casodex, Taxotere, and external beam radiation, but the initiation of vaccine therapy was equal to, or greater than, 30 days after the most recent therapy. Patients were treated in successive dose levels and aqueous vs. matrix cohorts, according to the protocol plan. We were able to administer the maximum permitted dose of 108 pfu without any serious adverse events by vaccination of the first of 18 patients. These initial 18 patients were followed throughout the one-year period after injection. An additional 14 patients were treated at the MTD dose level, as planned in the protocol and confirmed by a letter to the FDA. The purpose of the additional patients was to have sufficient numbers of patients in the groups to statistically evaluate the anti-PSA immune responses induced by the Ad/PSA vaccine. In summary, 32 patients were treated in the study followed through the one-year period. Two additional patients were enrolled in the study (total number of enrolled patients, 34) but never received the vaccine and were therefore not evaluable. One patient chose to have radiation therapy instead of participating in the trial and the second was diagnosed with a second malignancy (melanoma) shortly after his enrollment in the phase I study.

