7.5 Definitions of Response –

7.5.1 Primary Endpoint - PSA doubling-time response

- 7.5.1.1 Definition: a 50% increase in the PSADT compared to pre-enrollment PSADT.
- 7.5.1.2 PSADT will be calculated based on the MSKCC calculator, available at http://www.mskcc.org/mskcc/html/10088.cfm.
- 7.5.1.3 PSADT response will be measured at 9 and 18 months after initiation of the research intervention.
- 7.5.1.4 Three measurements of PSA, spaced at least 2 weeks apart, will be required prior to study enrollment. Post-intervention PSADT will be based on PSA levels at 3, 6 and 9 months (9 month PSADT calculation) and 3, 6, 9,12,15,18 month levels (18 month PSADT calculation).

7.5.2 Secondary Endpoint – PSA response

7.5.2.1 Definition: a 50% reduction in the pre-research intervention PSA value, verified with a second measurement >28 days later.

7.5.3 Progression:

Progression of disease is defined for 3 different categories of disease: measurable lesions; non-measurable/non-target lesions; and PSA-only disease. The first category of disease to progress will meet the definition of progression in this trial, as follows:

7.5.3.1 Progression for measurable disease:

Definition: Measurable lesions are defined as those that can be accurately measured in at least one dimension (longest diameter to be recorded) and is equal or greater than 20 mm with conventional techniques (CT, MRI, x-ray) or equal or greater than 10 mm with spiral CT scan. All tumor measurements must be recorded in millimeters (or decimal fractions of centimeters)

All measurable lesions (up to a maximum of 10) representative of all involved organs should be identified as target lesions and will be recorded and measured at baseline. Target lesions should be selected on the basis of their size (lesions with the longest diameter) and their suitability for accurate repetitive measurements (either by imaging techniques or clinically). A sum of the longest diameter (LD) for all target lesions will be calculated and reported as the baseline sum LD. The baseline sum LD will be used as reference to further characterize the objective tumor response of the measurable dimension of the disease.

All other lesions, including non-measurable small lesions as defined above and bone metastasis, will be identified as non-target lesions (see definition of progression for non-target lesions below).

Progression is defined if any of the criteria below are met:

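### The drug washout is counted to the first injection, not to the baseline PSA series, so the pre-enrollment PSADT that serves as the trial's only control can be measured on or across other therapy

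*Combined protocol and SAP*

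**What the plan says.** **Endpoint.** Section 7.5.1.1 defines the primary response: "Definition: a 50% increase in the PSADT compared to pre-enrollment PSADT". Section 7.5.1.4 sets the baseline: "Three measurements of PSA, spaced at least 2 weeks apart, will be required prior to study enrollment". It gives no maximum age for these values and no condition about other therapy. Post-vaccine PSADT uses months 3, 6 and 9 for the 9-month result, and months 3 to 18 for the 18-month result.

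**Entry.** Under 3.1.2, scan-positive men need "a PSA doubling time of ≥6 months, and a total PSA of <10 ng/ml, and asymptomatic". Scan-negative men enter with "a negative CT scan with any PSA doubling time and asymptomatic".

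**Washout.** Section 3.2.9 states: "Drugs such as Casodex or ketoconazole treatment must have been completed at least 6 weeks prior to initiation of treatment". I read initiation of treatment as injection 1; the term is not formally defined.

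**Other timing rules.** Section 3.1.7: "PSA used as an eligibility criterion must be drawn within 28 days prior to injection number 1", with a redraw on Day 1 as a baseline value. Section 4.7: "Patients must begin the vaccine protocol within 30 days of registration". Androgen deprivation continues throughout (Table 6, note 2).

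**Radiation.** Sections 3.1 and 3.2 contain no exclusion or interval for prior radiation. In Phase I (section 1.4), where external beam radiation was among the prior therapies, "the initiation of vaccine therapy was equal to, or greater than, 30 days after the most recent therapy".

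**The concern.** With no concurrent control, each man's pre-enrollment slope is the only yardstick for vaccine effect. If that slope is measured while he takes an antiandrogen or ketoconazole, or across the date he stops, part of the before-after difference belongs to the drug change. The same applies if radiation falls inside or just before the series. The washout rule looks as if it prevents this, but it protects the date of injection and not the PSAs from which the comparator is built. No passage links 3.2.9 to 7.5.1.4, and section 10 plans no adjustment or sensitivity analysis.

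Two things are at stake: the primary response rate, and, for scan-positive men only, whether the PSADT entry limit selects the men it is meant to select.

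**Working it through.** **1. The plan's own figures.** Section 10 gives a null rate of 0.30, a target of 0.50, alpha 0.1, power 0.8 and 32 patients for the Simon design. Exact enumeration reproduces the stated expected size and early-termination probability with a first stage that stops at 5 or fewer of 15, and success at more than 12 of 32: alpha 0.0997, power 0.804, early termination 0.722, expected size 19.73. (The printed first stage of 12 patients does not reproduce them; that is a separate matter.) For the one-stage design with n = 32, the cutoff that meets both error limits is 14 or more responders: type I error 0.069, power 0.811. The plan states no one-stage cutoff, so this one is derived. The sample size is not disputed here.

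**2. Do the windows permit an on-drug baseline?** Three PSAs at least 14 days apart span at least 28 days. If the drug stops on day -42 and registration is on day -30 (the 4.7 limit), 42 - 30 = 12 drug-free days precede enrollment. The latest possible PSAs are then on days -30, -44 and -58, so at least two of the three are on drug. If registration is on day -14 or later, at least 42 - 14 = 28 drug-free days remain and a clean series just fits, but nothing requires one. The 3.1.7 eligibility PSA is at least 42 - 28 = 14 days off drug, but it need not be one of the three.

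**3. Size of the error in one man.** Assumptions: log-linear PSA, least-squares slope, 30.44 days per month, no vaccine effect, and a therapy change that shifts only the third value. The formula inside the calculator named in 7.5.1.2 is not in the documents. For three equally spaced values, PSADT = ln 2 × span / (ln P3 - ln P1).

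- *Upward shift, 2-week spacing* (span 28 days = 0.920 months). A true 6-month PSADT gives a rise in ln PSA of 0.6931 × 0.920 / 6 = 0.1063. A reading of 4 months needs 0.6931 × 0.920 / 4 = 0.1594. The difference is 0.0531, and exp(0.0531) - 1 = 5.5%. If PSADT stays at 6 months after vaccination, 6/4 = 1.5, which is a response. The shift needed is 11.2% for a true PSADT of 3 months and 2.7% for 12 months.
- *Downward shift, weeks -12, -8, -4* (span 56 days = 1.840 months). A true 4-month PSADT gives a rise of 0.3188. A 15% fall in the third value adds ln 0.85 = -0.1625, leaving 0.1563, so PSADT reads 0.6931 × 1.840 / 0.1563 = 8.2 months and passes the entry limit. A 10% fall gives 5.97 months, just short of it. Here the comparator is inflated, so a response becomes harder to score.
- *Withdrawal effect after injection.* Baseline on a failing drug, PSADT 4 months. PSA is flat to month 6, then regrows at the old rate. Months 3, 6, 9: ln PSA rises by (3/4) ln 2 over 6 months, so PSADT = 6 / 0.75 = 8.0 months, +100%. Months 3 to 18 (six values, in units of ln 2: 0, 0, 0.75, 1.5, 2.25, 3.0): Sxx = 157.5, Sxy = 33.75, PSADT = 157.5 / 33.75 = 4.67 months, +17%, not a response. At 9 months, an effect ending at month 3, 4 or 5 gives 4.0, 4.8 or 6.0 months; only the last reaches +50%.

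**4. Trial level, as a scenario only.** One man moves the response rate by 1/32, about 3 points. With n = 32 and the derived cutoff of 14, suppose 10% of men have a contaminated baseline. If each of them has a false-response probability of 0.5 to 0.9, the null rate becomes 0.32 to 0.36 and type I error rises from 0.069 to 0.11-0.23. If contamination hides responses instead (response probability 0 to 0.3 in those men), power falls from 0.81 to 0.62-0.74. The documents give neither the fraction nor the probabilities.

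**The case against.** **A clean series may be the usual case.** Section 3.1.6 puts the eligibility laboratory values within two weeks of treatment, and Table 6 places most of them before registration. Together these push registration to about day -14 or later, where a clean series fits. This stands as far as it goes, although sections 8.2 to 8.4 count most of the same tests to study entry instead. It shows that contamination is permitted, not that it is certain.

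**The false responder is an extreme case.** A flat PSA to month 6 means a withdrawal effect of at least about 7.4 months (6 months plus 42 days). No passage describes such an effect, and section 10 places the primary efficacy determination at 18 to 20 months. This stands. A reader might infer that drug withdrawal readily creates responders at both time points, but in this scenario the 18-month result is not a response.

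**The secondary PSA response.** A reader might infer that the 50% PSA fall in 7.5.2.1 is exposed in the same way. The documents do not support that for drugs. If the Day 1 redraw in 3.1.7 is the reference, it is at least 6 weeks after the drug was stopped. Recent radiation is not covered by that argument.

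**Radiation is the weaker part.** The Phase I interval belongs to another trial and was also counted to vaccination. Entrants must be asymptomatic. The exclusion numbering skips 3.2.7, so the absence of a radiation criterion can be asserted only for the text available. No radiation effect is quantified here.

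**Noise.** A 28-day series is short. At a 6-month PSADT, ln PSA rises by 0.106, while an assumed 5-10% SD per measurement gives that rise a standard error of 0.07-0.14 (√2 × SD). Restricting the baseline can exchange bias for noise. That is a real cost of the fix.

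**Conclusion.** The point holds for the primary endpoint. Followed exactly, the plan allows the sole comparator to be built from PSAs drawn on, or across the stopping of, other PSA-active drugs, and the available text of section 3 gives no interval after radiation. The false-entry concern applies only to scan-positive men, since scan-negative men enter with any PSADT.

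Shifts of about 5% at 2-week spacing, or 15% over eight weeks, are enough to create an apparent response in one case and to pass the entry limit wrongly in the other. Those shifts are assumptions, as are log-linear growth and the absence of a vaccine effect. The direction of bias is not fixed, and the number of affected men is unknown. The documents therefore do not support saying that the response rate will be inflated, only that the plan cannot separate a vaccine effect from a change of therapy in such men. The gap should be closed.

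**What to change.** 1. In 7.5.1.4, state that the PSAs forming the comparator, and the PSADT used in 3.1.2, must be drawn on continuous castration and after other PSA-active drugs were stopped. Reconcile this with the washout anchor in 3.2.9.
2. Record the stop dates of prior drugs and radiation. Flag men whose baseline PSAs predate or straddle a stop, and report the 9- and 18-month response rates with and without them. For men already enrolled this needs only PSA dates and stop dates.
3. Ask the clinical team to reconcile section 3, which is silent on radiation, with the Phase I condition described in 1.4. No interval is proposed here.

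Cost: a short amendment and one sensitivity analysis. Some older PSA series become unusable, and recently treated men may wait longer for injection 1 or have a shorter, noisier baseline series.
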